Statistical Analysis Plan

An Open-label, Parallel-Group Study to Evaluate the
Pharmacokinetics of Lemborexant and Its Metabolites in Subjects
with Normal Renal Function or with Severe Renal Impairment

Protocol Number: E2006-A001-105

Version 2.0

Issue Date: 08-AUG-2018

Authors: PPD [REDACTED]

PPD [REDACTED]

Previous Versions

Version 1.0 25-MAY-2018

SAP Amendments before database lock

Version	Issue Date	Section	Revision/Addition	Rationale
2.0	08-AUG-2018	6.1.2	Definition of Pharmacokinetic Analysis Set updated	The definition of the PK analysis set was edited for consistency with the hepatic impairment study.
		3.1, 6.2.2, 6.15 and 12	Calculation of PK parameter AUC ₍₀₋₈₎ added. AUC ₍₀₋₈₎ included in all listings, summary statistics, figures and statistical analysis tables. Box plots of AUC ₍₀₋₈₎ added (Figure 14.2.2.7)	AUC _(0-8h) was added to represent the total exposure over the time the subject would be sleeping.
		6.2.2 and 6.15	Calculation of AUC _u added for metabolites as well as lemborexant. Descriptive statistics for unbound fraction protein AUC _u of lemborexant and metabolites added (Table 14.2.2-5 and Table 14.2.3.5). Boxplots added (Figure 14.2.2.11)	AUC _u was calculated for metabolites to assess changes in protein binding of each metabolite over time after dosing.
		6.15	Scatterplots for PK parameters by renal impairment group added (Figure 14.2.2.12)	Scatterplots for PK parameters vs. renal impairment were added for consistency with the hepatic impairment study. Scatterplots represent a visual assessment of how drug exposure is affected by renal impairment.
		6.15	Scatterplots for PK parameters adjusted by Unbound Fraction added (Figure 14.2.2.13)	Scatterplots for PK parameters adjusted by unbound fraction vs. renal impairment were added for consistency with the hepatic impairment study. Scatterplots represent a visual assessment of how

				unbound drug exposure is affected by renal impairment.
		6.15	Mean profiles for PK concentration data truncated to 24 hours added (Figure 14.2.22)	Mean profiles were truncated to 24 h in order to better assess the concentration time profile during the first 24 hours of exposure.
		6.2.2	Molecular weights for lemborexant and metabolites added into definition of MPR $AUC_{(0-inf)}$	MPR was molecular-weight corrected to better assess direct comparisons of total exposure for metabolite and parent.

1 INTRODUCTION

This document details the planned statistical analyses for the Eisai protocol E2006-A001-105.

The proposed analyses are based on the contents of V2.0 of the protocol (dated 02 April 2018).

This is a multi-center, single dose, open-label, parallel-group study in subjects with severe renal impairment and matched (with regard to age [± 10 years], race, sex, and body mass index [BMI, $\pm 20\%$]) healthy control subjects. The study will be conducted in 2 phases: Prerandomization Phase (containing the Screening Period and Baseline Period [Day -1]) and a Treatment Phase. The Screening Period will last up to 20 days, the Baseline Period will be 1 day, and the Treatment Period will be 11 days. Subjects will remain in the clinic until approximately 7 days after dosing (will be discharged from clinic after the Day 8 pharmacokinetic (PK) blood draw) and will return on Day 11 for end-of-study assessments/study discharge.

Subjects will be assigned to 1 of 2 groups: Subjects with severe renal impairment will be Group 1, and subjects with normal renal function demographically matched to subjects with severe impairment will be Group 2. The number of subjects per group and estimated glomerular filtration rate (eGFR) values used to assign each subject to a renal function group are shown below:

Classification of Renal Function Study Groups		
Population	eGFR ^a (mL/min/1.73 m ²)	Number of Subjects per Group
Group 1: Severe renal impairment	<30 and not on dialysis	8
Group 2: Normal renal function	≥ 90	8

^a Day -1 estimated glomerular filtration rate (eGFR) will determine the renal category group to which a subject is assigned. If the Day -1 eGFR value places the subject into a different renal category group from that calculated at screening, the value can be repeated once within 24 to 48 hours. If eGFR variability across these scheduled and repeat time points indicates the subject does not consistently meet the criteria for one renal category group, subject enrollment into a renal category group will be at the discretion of the Medical Monitor and investigator, in consultation with the sponsor.

The eGFR is determined by the Modification of Diet in Renal Disease (MDRD) formula:

$$MDRD \text{ formula } (mL/min/1.73m^2) = 175 \times (\text{serum creatinine})^{-1.154} \times (\text{age})^{-0.203} \times (0.742 \text{ if female}) \times (1.212 \text{ if African American})$$

Group 1 subjects (severe renal impairment) will be enrolled first. Group 2 subjects (normal renal function) will be matched according to age, race, sex, and BMI.

Subjects determined eligible for study participation will receive a single 10 mg oral dose of lemborexant on Day 1. During the Treatment Period, plasma will be obtained over 11 days for the determination of lemborexant and metabolite concentrations M4, M9 and M10. Standard safety assessments will be measured before, during, and at the conclusion of the study.

2 STUDY OBJECTIVES

2.1 Primary Objective

- To assess the effect of severe renal impairment on the PK of lemborexant after a single dose administration.

2.2 Secondary Objectives

- To assess the effect of severe renal impairment on the PK of the unbound fraction of lemborexant.
- To assess the effect of severe renal impairment on the PK of metabolites (M4, M9, and M10) of lemborexant.
- To assess the safety and tolerability of lemborexant in subjects with normal renal function or with severe impaired renal function.

3 ENDPOINTS

3.1 Pharmacokinetic Endpoints

The endpoints are PK parameters derived by noncompartmental analysis using plasma concentrations of lemborexant and its metabolites. These parameters include, but are not limited to: C_{max} , t_{max} , $AUC_{(0-8h)}$, $AUC_{(0-72h)}$, $AUC_{(0-t)}$, $AUC_{(0-inf)}$, AUC_{ex} , $t_{1/2}$, CL/F , V_z/F , MPR , $AUC_{(0-inf)}$, fu , AUC_u , and CL_u/F . PK parameters are defined in Section 6.2.2.

$AUC_{(0-72h)}$, $AUC_{(0-t)}$, $AUC_{(0-inf)}$, and C_{max} of lemborexant are the primary PK parameters. The rest of the parameters including the PK parameters of the metabolites, will be secondary endpoints.

3.2 Safety Endpoints

Safety will be assessed by monitoring and recording all adverse events (AEs) and serious adverse events (SAEs), regular monitoring of hematology and blood chemistry, regular measurement of vital signs, electrocardiograms (ECG) and the performance of physical examinations.

4 SAMPLE SIZE

A sample size of 8 subjects for each cohort is based on the recommendations in Food and Drug Administration Guidance 10, and should provide estimates to assess whether dose adjustment is required for subjects with renal impairment.

Based on data from single dose studies of the 10 mg tablet (E2006-A001-004, E2006-A001-005, and E2006-A001-008), the pooled between-subject standard deviation of logarithmically transformed $AUC_{(0-\text{inf})}$ values of lemborexant is 0.391. With a sample size of 8 subjects with severe renal impairment and 8 matched controls, the 2-sided 90% confidence interval (CI) for the geometric mean ratio for $AUC_{(0-\text{inf})}$ would extend from 0.72 to 1.38 (for a mean ratio of 1.0). Similar precision is expected for the 2-sided 90% CI for the ratio for $AUC_{(0-t)}$.

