PK parameters will be summarized overall by treatment and by treatment stratified by analyte and group using descriptive statistics (n, mean, SD, min, median, max, geometric mean, CV%, calculated as: $\sqrt{\exp[\text{std}^2 \text{ of log transformed data}] - 1} * 100$).

The rules for presenting raw individual values and summary statistics for PK concentration and parameter data are provided in Section 6.3.1.

Protein Binding

Blood samples for plasma protein binding for lemborexant and metabolites will be collected for each subject at 2 time points: 1 hour and 24 hours postdose. Protein binding data will be provided by the vendor to Worldwide Clinical Trials as a percentage; if more than one value is available for either time point, the average of the protein binding values will be used in the calculations. Protein binding results will be presented as fractions and percentages and will be summarized for each time point (1 hour and 24 hour). Additionally, the average of the 2 timepoints (1 hour and 24 hour) will be calculated for each subject and summarized. The average of the 1 hour and 24 hour timepoints will be used to calculate the unbound PK parameters (AUC_u and CL_u/F).

Protein binding results for 1 h and 24 h will be summarized using the following descriptive statistics: n, mean, SD, minimum, median, and maximum. Protein binding results (averaged timepoints at 1 h and 24 h) will be summarized using the following descriptive statistics: n, mean, SD, CV%, minimum, median, maximum, and geometric mean.

Box plots will be created for the percent bound comparing lemborexant and metabolites across groups. Scatterplots will also be created for lemborexant and metabolite AUC_u adjusted by the unbound fraction in plasma.

Evaluation of the impact of renal impairment on drug exposure:

The effect of renal impairment on the PK of lemborexant will be assessed using a linear model with renal impairment group as a factor. Logarithmically transformed values of the primary PK parameters C_{\max} , AUC_(0-8h), AUC_(0-72h), AUC_(0-t), and AUC_(0-inf) will be utilized to estimate the geometric mean ratio (and two-sided 90% confidence intervals) of subjects with severe renal impairment versus subjects with normal renal function. Similar statistical analyses will be conducted for the PK parameters of the metabolites and unbound lemborexant. In addition,

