16.2.6.1	Lemborexant and Metabolites Concentration-Time and Protein Binding Data Listing by Subject Safety Analysis Set
16.2.6.2	Lemborexant Pharmacokinetic Parameter Listing by Subject PK Analysis Set
16.2.6.3	M4, M9, and M10 Pharmacokinetic Parameter Listing by Subject PK Analysis Set
16.2.6.4	Terminal Elimination Rate of Lemborexant and Metabolites for Individual Subjects after Administration of Lemborexant 10 mg to Subjects Severe Renal Impairment (Group 1) or Normal Renal Function (Group 2) PK Analysis Set

- 16.2.6.5 PK Text Output
- 16.2.6.6 ANOVA SAS Output Text

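### SAP Section 4: the expected 90% CI of 0.72 to 1.38 fits a normal multiplier; the planned two-group model on 14 df gives 0.71 to 1.41 at the same SD

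*SAP*

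**What the plan says.** SAP Section 4 takes the group size from guidance: "A sample size of 8 subjects for each cohort is based on the recommendations in Food and Drug Administration Guidance 10". It then describes the precision that this size should give. The log-scale between-subject SD for AUC(0-inf), pooled over three earlier single-dose studies of the 10 mg tablet, is put at 0.391. From this SD and two groups of 8, the section forecasts the two-sided 90% interval for the ratio of geometric means, which "would extend from 0.72 to 1.38 (for a mean ratio of 1.0"). It expects similar precision for AUC(0-t). No multiplier or degrees of freedom are given.

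Section 6.15 defines the analysis that will produce the reported interval. The effect of renal impairment on lemborexant PK "will be assessed using a linear model with renal impairment group as a factor", fitted to log-transformed parameters and reported as geometric mean ratios with two-sided 90% CIs. No other factor, covariate or matching term is named. In Section 12, Listing 16.2.6.6 is titled "ANOVA SAS Output Text".

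**The concern.** A forecast of the CI should describe the interval that the planned analysis will deliver. A two-group linear model on 16 subjects estimates its residual variance on 14 df, so its 90% CI uses a t multiplier. Section 4's limits are narrower than that multiplier gives at Section 4's own SD, and they agree with the normal multiplier.

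This is the only numeric statement of expected precision in the SAP, and it is carried over to AUC(0-t) as well. Anyone who later compares achieved with planned precision would start from a figure that the planned model does not produce at the planning SD.

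**Working it through.** **Inputs**
- Log-scale between-subject SD: 0.391 (Section 4).
- Subjects: 8 + 8 (Section 4).
- Interval: two-sided 90%, so 5% in each tail (Section 4).
- Assumed ratio: 1.0 (Section 4).
- Model: renal group as the only named factor (Section 6.15), so residual df = 16 − 2 = 14 if all 16 subjects contribute.

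**Standard error of the log ratio**

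SE = SD × √(1/8 + 1/8) = 0.391 × 0.5 = 0.1955.

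**Reproducing the stated figure**

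The limits are exp(± m × SE). With the normal multiplier m = 1.6449, the half-width is 1.6449 × 0.1955 = 0.3216, and the limits are 0.7250 and 1.3793. The upper limit rounds to 1.38. The lower limit at an SD of exactly 0.391 is 0.72501, which strictly rounds to 0.73. The printed 0.72 fits truncation or an unrounded SD slightly above 0.391 (SD 0.3915 gives 0.7247 to 1.3799).

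**The planned model**

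t(0.95, 14 df) = 1.7613. The half-width is 1.7613 × 0.1955 = 0.3443, and the limits are 0.7087 and 1.4111, or 0.71 to 1.41. Ratio of half-widths: 0.3443 / 0.3216 = 1.071.

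**Multiplier implied by the printed limits**

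Allow the SD to lie between 0.3905 and 0.3915 and both limits to be rounded to two decimals.
- Smallest multiplier: −ln(0.725) / (0.3915 × 0.5) = 1.643.
- Largest multiplier: ln(1.385) / (0.3905 × 0.5) = 1.668.

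The value for 14 df, 1.761, lies outside this range.

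**Other routes to 0.72 to 1.38**

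| Variant | 90% limits |
|---|---|
| t, 14 df, SD 0.3905 | 0.709 to 1.410 |
| t, 14 df, SD 0.3915 | 0.708 to 1.412 |
| Paired, t, 7 df, same SE | 0.690 to 1.448 |
| 0.391 read as a CV (log SD 0.377), t, 14 df | 0.717 to 1.394 |
| 0.391 read as a CV, normal | 0.733 to 1.364 |
| t, 80 df, SD 0.391 | 0.722 to 1.384 |

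Only a multiplier with many df gives the printed limits. Under t with 14 df, an upper limit that rounds to 1.38 needs an SD of 0.362 to 0.370. At SD 0.391, a t-based two-group interval reaches 0.725 to 1.380 with 9 subjects per group.

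**The case against.** The strongest reply is that nothing is miscalculated. The stated limits follow from the stated inputs by a standard large-sample formula. Section 4 does not claim a t distribution and Section 6.15 names no multiplier, so no two sentences contradict each other. What stands of this is that the fault is an unstated approximation and not a slip in the sums. The printed interval is still not the one that the planned model gives at that SD.

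Second, the source of the figure is inferred. The implied range of 1.643 to 1.668 also admits a t multiplier with about 67 or more df, and the SD was pooled over three studies, so their df may have been used. That cannot be ruled out, because the SAP does not give those df. They would not be the planned model's df in any case.

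Third, the shift is small beside the uncertainty of any such forecast. If the true SD is 0.391, the sample SD on 14 df lies between 0.685 and 1.301 times that value with 90% probability. The realised log half-width then runs from 0.344 × 0.685 = 0.236 to 0.344 × 1.301 = 0.448. There is about a 41% chance that the realised interval is no wider than the one stated. This is correct and is a reason to rate the point low. It does not justify centring the forecast on the wrong multiplier.

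Fourth, 0.71 to 1.41 is itself the interval at a sample SD of exactly 0.391. On average the sample SD is 0.982 of the true one, so the mean half-width is 0.344 × 0.982 = 0.338, or 0.71 to 1.40. That is still wider than stated.

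**Conclusion.** The point holds. At the SAP's own SD and group sizes, the planned model gives a 90% CI of 0.71 to 1.41, against the stated 0.72 to 1.38. The log half-width is about 7% larger than stated.

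This rests on two assumptions: that renal group is the only term in the model, as Section 6.15 states, and that all 16 subjects contribute AUC(0-inf). Section 6.2.2 allows AUC(0-inf) to go unreported when the terminal slope is unreliable. At the same SD, fewer contributing subjects would only widen the interval. That the figure came from a normal multiplier is inferred; that it does not match 14 df is not.

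The importance is low. Section 4 rests the group size on guidance, the SAP sets no numeric no-effect bounds, and the follow-up regression in Section 6.15 depends on the observed interval and not on this forecast. No decision changes.

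**What to change.** Restate the sentence in Section 4 along these lines: using the t distribution with 14 df, SD 0.391 and all 16 subjects contributing, the two-sided 90% CI for the AUC(0-inf) ratio would extend from 0.71 to 1.41 at a ratio of 1.0. If the sponsor prefers to keep 0.72 to 1.38, the minimum is to say that it is a normal approximation treating the SD as known, and to add that the planned model would give a slightly wider interval.

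The cost is one sentence in the SAP, with no change to design, sample size or analysis.

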5 RANDOMIZATION

Not Applicable.

6 PLANNED ANALYSES

No statistical analysis plan (SAP) prepared in advance of the data can be absolutely definitive and the final clinical study report (CSR) may contain additional tables or statistical tests if warranted by the data obtained. The justification for any such additional analyses will be fully documented in the final CSR.

6.1 Analysis Sets

6.1.1 Enrolled Subjects

A subject is considered to be enrolled in the study if they have provided informed consent.

6.1.2 Pharmacokinetic (PK) Analysis Set

The PK Analysis Set is the group of subjects who dosed with the test drug and

6.1.3 had sufficient PK data to derive at least 1 PK parameter. Safety Analysis Set

The Safety Analysis Set is the group of subjects who dosed with the test drug and had at least 1 postdose safety assessment.

6.2 Derived Data

This section describes the derivations required for statistical analysis. Unless otherwise stated, variables derived in the source data will not be re-calculated.

6.2.1 Race

Where more than one race category has been selected for a subject, these race categories will be combined into a single category labeled “Multiple” in the summary tables. The listings will reflect the original selected categories.

6.2.2 Pharmacokinetic Parameters

Concentration time data for lemborexant and its metabolites will be provided following database lock and will be analyzed by non-compartmental methods using PhoenixTM WinNonlin[®] (Version 6.3 or later, Certara USA, Inc., Princeton, NJ), in accordance with Eisai 302-104.00-MNL Non-Compartmental Pharmacokinetic Analysis (effective date 08 Jun 2016).

Concentrations that are below the limit of quantification (BLQ) will be treated in accordance with Section 2.5.1 of Eisai 302-104.00-MNL. During the pharmacokinetic analysis, BLQ values at predose up to the first quantifiable concentration will be set to zero; BLQ values between 2 quantifiable concentrations will be set to “missing”; and quantifiable concentrations preceded by 2 consecutive BLQ values in the terminal phase will be set to “missing”.

The following PK parameters will be calculated for lemborexant and its metabolites (as data permit):

C_{\max}	Maximum plasma concentration determined directly from individual concentration-time data, reported to 3 significant figures
t_{\max}	Time to reach maximum plasma concentration determined directly from individual concentration-time data, reported to 2 decimal places
$AUC_{(0-8h)}$	Area under the plasma concentration–time curve from time zero to 8 hours postdose; calculated using the linear-log trapezoidal rule (linear-up log-down), reported to 3 significant figures
$AUC_{(0-72h)}$	Area under the plasma concentration–time curve from time zero to 72 hours postdose; calculated using the linear-log trapezoidal rule (linear-up log-down), reported to 3 significant figures
$AUC_{(0-t)}$	Area under the plasma concentration–time curve from time zero to the time of the last quantifiable concentration; calculated using the linear-log trapezoidal rule (linear-up log-down), reported to 3 significant figures
$AUC_{(0-inf)}$	Area under the plasma concentration–time curve extrapolated to infinity, reported to 3 significant figures and calculated as:

	$AUC_{(0-\text{inf})} = AUC_{(0-t)} + C_{\text{last}}/\lambda_z$
AUC_{ex}	The percentage of $AUC_{0-\text{inf}}$ based on extrapolation, reported to 3 significant figures and calculated as: $\%AUC_{\text{ex}} = (AUC_{(0-\text{inf})} - AUC_{(0-t)})/AUC_{(0-\text{inf})} * 100$
$t_{1/2}$	The observed terminal elimination half-life, calculated as: $t_{1/2} = \ln(2)/\lambda_z$; see additional criteria below, reported to 3 significant figures
λ_z	The observed elimination rate constant; estimated by linear regression through at least three data points (not including t_{max}) in the terminal phase of the log concentration-time profile; see additional criteria below, reported to 3 significant figures
CL/F	Apparent body clearance, reported to 3 significant figures and calculated as: $CL/F = \text{Dose}/AUC_{(0-\text{inf})}$; calculated for lemborexant only
V_z/F	Apparent volume of distribution based on the terminal phase, reported to 3 significant figures and calculated as: $\text{Dose}/(\lambda_z \times AUC_{(0-\text{inf})})$; calculated for lemborexant only
MPR $AUC_{(0-\text{inf})}$	Ratio of $AUC_{(0-\text{inf})}$ of individual metabolite to $AUC_{(0-\text{inf})}$ of lemborexant, corrected for molecular weights (E2006 = 411; M4, M9, and M10 = 427), reported to 3 significant figures
fu	plasma protein unbound fraction, reported to 3 significant figures
AUC_u	$AUC_{(0-\text{inf})}$ values adjusted by unbound fraction in plasma, reported to 3 significant figures
CL _u /F	Apparent clearance relative to the unbound plasma concentration based on AUC_u , reported to 3 significant figures (for lemborexant only)

At least 3 time points with quantifiable plasma concentrations will be required for the calculation of $AUC_{(0-t)}$. Individual $AUC_{(0-\text{inf})}$ values for which $AUC_{\text{ex}} > 20\%$ will be retained in the end of text tables and will not be included in the summary statistics. Individual $AUC_{(0-\text{inf})}$ values for which $AUC_{\text{ex}} > 20\%$ may be included in the summary statistics if approved by the Sponsor.

At least 3 time points (of which the first time point must be greater than t_{max}) with quantifiable plasma concentrations will be required for the calculation of λ_z .

No value for λ_z and other λ_z -related parameters ($AUC_{(0-\text{inf})}$, $t_{1/2}$, CL/F, etc.) will be reported for lemborexant and its metabolites if the PK Analyst or the Sponsor decides a reliable estimate of λ_z is not possible after considering the following factors:

- 1) The duration of time over which λ_z is estimated (λ_z range) is less than twice the subsequently estimated terminal elimination phase half-life ($t_{1/2}$).
- 2) The adjusted regression coefficient (R^2 adj) is not ≥ 0.90 ; and
- 3) The concentration profiles do not exhibit a terminal elimination phase in the concentration versus time profile.
- 4) If the % extrapolation is > 20 , related parameters $AUC_{(0-\text{inf})}$, CL/F, and V_z/F will be reported based on the pharmacokineticist's judgment.

6.2.3 Baseline

Baseline for the safety variables is defined as the last nonmissing value (either scheduled, unscheduled or repeat) before the subject receives the dose of lemborexant on Day 1. For laboratory variables, only results provided by the Worldwide Clinical Trials laboratory will be used as baseline values.

